9.8 Adverse Event Reporting

It is a requirement that the Investigator promptly reports all SAEs (irrespective of relationship) to [REDACTED] as soon as possible, but no later than 24 hours after becoming aware of the event occurring.

SAE reports must be communicated as follows:

Attn: Medical Monitor

Category	Approx. Number of Samples
1	100
2	150
3	120
4	180
5	100
6	200
7	150
8	120
9	180
10	100

Suspected, unexpected serious adverse drug reactions (SUSARs) will be reported to the FDA, all relevant competent authorities, and IRBs/Ethics Committees within the required timeframes of seven calendar days for SUSARs that are fatal or life-threatening, and fifteen calendar days for all other SUSARs by the Sponsor.

All other Adverse Events (AEs) must be reported (entered) into the RAVE EDC clinical trial database (electronic case report form (eCRF) within two weeks from the date the site becomes aware of the AE.

10. DEVICE COMPLAINT HANDLING

If a device failure occurs with the applicator device, tips or regulators, a Device Complaint Form must be completed and faxed immediately (within 24 hours to [REDACTED]). Included are those complaints related to the applicator devices, tips or regulators that have been open but unused (e.g. sterile container was opened inadvertently). Upon receipt of the Complaint Form, instructions will be given on handling/returning of the defective device.

11. REGULATORY OBLIGATIONS

11.1 Informed Consent

Prior to participation, the study procedures and any known or likely risks will be explained to the subjects (as applicable) and/or their parent or legal guardian by the investigator or other qualified study personnel. An Informed Consent Form and patient information leaflet, as applicable, will also be provided containing all the required information. Any questions will be answered and the patient and/or their parent or legal guardian will then be given sufficient time to consider their participation in the study before signing a consent form. For paediatric subjects who possess the intellectual and emotional ability to comprehend the concepts involved in the trial, must also give their assent to participate in the study. An age appropriate patient leaflet/assent will be provided. Subjects and/or their parent or legal guardian should receive a copy of the Informed Consent Form.

The Investigator (or designee) will explain that the subjects and/or parent or legal guardian are completely free to refuse to enter the study or to withdraw from it at any time, without any consequences for their further care and without the need to justify.

Each subject and/or their parent or legal guardian will be informed that the subject's source medical records may be checked by representatives from the Sponsor or from a regulatory agency, in accordance with applicable regulations. However, they should be made aware that all information will be treated with confidentiality, and a study ID code or number will identify them.

11.2 Investigational Review Boards / Ethics Committees

The investigator must submit the Protocol and the Consent Form to the appropriate IRB/EC according to local requirements. Approval from the IRB/EC must be obtained prior to starting any study-related procedure.

12 Data Management

12.1 Electronic Data Capture (EDC)

An EDC system will be utilized by trial site personnel to transfer trial data from source records (medical records and/or source document worksheets) onto common eCRFs (electronic Case Report Forms). This system is a web-based, secure electronic software application. This system was designed and is developed and maintained by [REDACTED] in a manner that is compliant with national and international GCP data protection/data privacy and electronic record/electronic signature (e.g., 21 CFR Part 11) regulatory requirements. The EDC system will be used to facilitate the collection of all trial data at the site. Designated site personnel will be responsible for entering patient data into the EDC system. All external and Sponsor internal users will be trained on the EDC application at a level dependent on their planned function. An EDC digital User Manual will be available under the help menu within the [REDACTED] website to assist in the collection and entry of source data into the electronic casebook. A 24/7/365 Help Desk Support line staffed by the outsourced vendor will be available to respond to site and monitor questions.

12.2 Data Collection

The Investigator must maintain required records on all study subjects. Data for this study will be recorded in the subject's medical records, study-specific worksheets, and on eCRFs provided by the Sponsor in accordance with the parameters set forth in ICH Topic E6 for GCP (1.5.96) Guidelines – Responsibilities of Sponsor, Monitor, and Investigator and applicable regulations. All data on the CRFs should be recorded from appropriate source documentation.

Each EDC eCRF will be completed by the PI or PI's designee. Every effort should be made to respond to all monitoring and/or data management questions on each eCRF as completion of the data is required by the protocol. A unique ID number will identify each subject. At no time should the subject name appear on the eCRFs. Complete data is needed in order to provide statistical analysis for each subject. All data should be recorded accurately and completely. The investigator is responsible for reviewing and approving each completed eCRF. Assurance of overall review and approval will be documented by the Investigator electronically signing each subject's electronic casebook.

12.3 Data Correction

Required data corrections to eCRFs will be prompted via automated electronic edit checks and/or queries manually created by sponsor reviewers. The change(s), individual making the change(s), and time the change(s) were made to the eCRFs will be automatically captured in the audit trail within [REDACTED].

12.4 Source Documentation

Investigators must keep accurate separate records (other than the eCRFs) of all subjects' visits, being sure to include all pertinent study related information. A statement should be made indicating that the subjects have been enrolled in Protocol and have provided written Informed Consent. Any and all side effects and adverse events must be thoroughly documented. Results of any diagnostic tests conducted during the study should also be included in the source documentation. Telephone conversations with the subjects concerning the study must also be recorded.

The Investigator is responsible for maintaining a Subject Identification Log, which will include all subjects who provided informed consent (i.e. to include randomized subjects and screening failures). This confidential subject identification code provides the link between named subject source records in the subject file and anonymous eCRF data provided to ETHICON.

The Investigator must retain all study related documentation until at least two years after the final marketing application is approved, or at least two years have elapsed since the formal discontinuation of the clinical study. Study documents should not be destroyed without prior written agreement between the Investigator and ETHICON. The sponsor must be notified if the Investigator wishes to assign the study records to another party, or move them to another location.

13 SPONSOR OBLIGATIONS

13.1 Monitoring

The Sponsor monitor will contact and visit the Investigator regularly and will be allowed, on request, to inspect the various records of the trial. The monitor will visit as soon as possible following enrollment of the first subject and at regular intervals during the study (approximately every four to six weeks) as deemed necessary. It will be the monitor's responsibility to inspect the eCRFs at regular intervals throughout the study, to verify the adherence to the protocol and the completeness, correctness and accuracy of all eCRF entries. The study monitor will have access to laboratory test reports and any other source records and data needed to verify the entries on the eCRFs, unless restricted by local laws. The Investigator agrees to cooperate with the study monitor to ensure that any problems detected in the course of these monitoring visits are resolved.

13.2 Regulatory Requirements

This study will be conducted in accordance with specific provisions of the associated IRB/IECs, and in accordance with the ethical principles that have their origin in the Declaration of Helsinki, and that are consistent with Good Clinical Practice (GCP) and the applicable national and regional regulatory requirement(s).

13.3 Liability and Insurance Conditions

In case of any damage or injury occurring to a subject in association with the trial medication or participation in the study, ETHICON has provided insurance cover. A copy of this policy is on file at ETHICON.

14 INVESTIGATOR OBLIGATIONS

14.1 Audit and Inspection

The Investigator will make source data and documents for this study available to an appropriately qualified quality assurance auditor mandated by ETHICON, or to regulatory authority inspectors, after appropriate notification.

14.2 Confidentiality of Subject Records

The Investigator will ensure that the subjects' anonymity will be maintained. On eCRFs or other study documents submitted to ETHICON, subjects will not be identified by their names, but by an identification code *that may consist of a combination of the site, and randomization or enrollment number*. Documents not for submission to ETHICON i.e. the Subject Identification Log and original subjects' consent forms will be maintained in the Investigator Site File.

14.3 Record Retention

The Investigator will maintain all eCRFs and all source documents that support the data collected from each subject, and all trial documents as specified by applicable regulatory requirement(s). The Investigator will take measures to prevent accidental or premature destruction of these documents. Essential documents must be retained until at least 2 years after the last approval of a marketing application worldwide, or until at least 2 years have elapsed since the formal discontinuation of clinical development of the investigational product. These documents will be retained for a longer period if required by the applicable regulatory requirements or by an agreement with ETHICON. It is the responsibility of ETHICON to inform the Investigator as to when these documents no longer need to be retained. If the responsible Investigator retires, relocates, or for other reasons withdraws from the responsibility of keeping the study records, custody must be transferred to a person who will accept the responsibility. ETHICON must be notified in writing of the name and address of the new custodian.

15 CHANGES TO THE PROTOCOL

15.1 Protocol Amendments

All protocol amendments are required to be submitted for information/consideration to the regulatory authorities, IRBs and ECs.

15.2 Clinical Trial Termination

Both the Investigator and ETHICON reserve the right to terminate the study at any time. Should this be necessary, the procedures will be arranged on an individual study basis after review and consultation with both parties. In terminating the study, ETHICON and the Investigator will ensure that adequate consideration is given to the protection of the subjects' interests and safety.

15.3 Use of Information and Publication

[figure not shown]
All information concerning study data, ETHICON's operations, patent application, formulas, manufacturing processes, basic scientific data, and formulation information, supplied by the Sponsor or Sponsor designee to the investigator and not previously published, is considered confidential and remains the sole property of ETHICON. The Investigator agrees to use this information only to accomplish this study and will not use it for other purposes without the sponsor's written consent.

The Investigator understands that the information developed in the clinical study will be used by ETHICON in connection with the continued development of the EVICEL® product, and thus may be disclosed as required to other clinical investigators or government regulatory agencies. To permit the information derived from the clinical studies to be used, the Investigator is obligated to provide the sponsor with all data obtained in the study.

Any publication or other public presentation of results from this study requires prior review by ETHICON. Draft abstracts, manuscripts, and materials for presentation at scientific meetings must be sent to the sponsor at least 30 working days prior to abstract or other relevant submission deadlines. Authorship of publications resulting from this study will be based on generally accepted criteria for major medical journals.

The investigator understands not to use the name of ETHICON, EVICEL®, or any its employees, in any publicity, news release or other public announcement, written or oral, whether to the public, press or otherwise, relating to this protocol, to any amendment hereto, or to the performance hereunder, without the prior consent of ETHICON.

ETHICON CONTACT DETAILS

Appendix 1: CDC/NHSN Criteria for Defining a Surgical Site Infection (SSI)

Superficial Incisional SSI

Infections occur within 30 days after the operation *and* infection involves only skin or subcutaneous tissue of the incision *and* at least *one* of the following:

1. Purulent drainage, with or without laboratory confirmation, from the superficial incision.
2. Organisms isolated from an aseptically obtained culture or fluid or tissue from the superficial incision.
3. At least one of the following signs or symptoms of infection: pain or tenderness, localized swelling, redness, or heat *and* superficial incision is deliberately open by surgeon, *unless* incision is culture-negative.
4. Diagnosis of superficial incisional SSI by the surgeon or attending physician.

Do *not* report the following conditions as SSI:

1. Stitch abscess (minimal inflammation and discharge confined to the points of suture penetration).
2. Infection of an episiotomy or newborn circumcision site.
3. Infected burn wound.
4. Incisional SSI that extends into the fascial and muscle layers (see deep incisional SSI).

Note: Specific criteria are used for identifying infected episiotomy and circumcision site and burn wounds.

Deep Incisional SSI

Infections occurs within 30 days after the operation if no implant is left in place or within 1 year if implant is in place and the infection appears to be related to the operation *and* infection involves deep soft tissues (e.g., fascial and muscles layers) of the incision *and* at least *one* of the following:

1. Purulent drainage from the deep incision but not from the organ/space component of the surgical site.
2. A deep incision spontaneously dehisces or is deliberately opened by a surgeon when the patient has at least one of the following signs or symptoms: fever ($>38^{\circ}\text{C}$), localized pain, or tenderness, unless site is culture-negative.
3. An abscess or other evidence of infection involving the deep incision is found on direct examination, during reoperation, or by histopathologic or radiologic examination.
4. Diagnosis of a deep incisional SSI by a surgeon or attending physician.

Notes:

1. Report infection that involves both superficial and deep incisional sites as deep incisional SSI.
2. Report organ/space SSI that drains through the incision as a deep incisional SSI.

Organ/space SSI

Infections occurs within 30 days after the operation if no implant is left in place or within 1 year if implant is in place and the infection appears to be related to the operation *and* infection involves any part of the anatomy (e.g., organs or spaces) other than the incision, which was opened or manipulated during an operation *and* at least *one* of the following:

1. Purulent drainage from a drain that is placed through a stab wound into the organ space.
2. Organisms isolated from an aseptically obtained culture of fluid or tissue in the organ/space.
3. An abscess or other evidence of infection involving the organ/space that is found on direct examination, during reoperation, or by histological or radiologic examination.
4. Diagnosis of an organ/space SSI by a surgeon or attending physician.

Appendix 2: U.S. Center for Disease Control (CDC) Guideline for Prevention of SSI Surgical Wound Classification

CLASS I/CLEAN:

An uninfected operative wound in which no inflammation is encountered and the respiratory, alimentary, genital and urinary tracts are not entered. Clean wounds are primarily closed and, if necessary, drained with closed drainage. Operative incisional wounds that follow non-penetrating (blunt) trauma should be included in this category if they meet these criteria.

CLASS II/CLEAN-CONTAMINATED:

An operative wound in which the respiratory, alimentary, genital and urinary tract is entered under controlled conditions and without unusual contamination. Specifically, operations involving the biliary tract, appendix, vagina, and oropharynx are included in this category, provided no evidence of infection or major break in technique is encountered.

CLASS III/CONTAMINATED:

Open, fresh, accidental wounds, operations with major breaks in sterile technique or gross spillage from the gastrointestinal tract, and incisions in which acute, nonpurulent inflammation is encountered.

CLASS IV/DIRTY OR INFECTED:

Old traumatic wounds with retained devitalized tissue and those that involve existing clinical infection or perforated viscera. This definition suggests that the organisms causing postoperative infection were present in the operative field before the operation.

Appendix 3: Flow Chart for Intra-operative Watertight Dural Closure Assessment during Surgical Procedure

1. STUDY OBJECTIVES

The objective of this study is to evaluate the safety and efficacy of EVICEL® (EVICEL) when used for suture-line sealing in dura-mater closure in elective or urgent paediatric cranial neurosurgery to provide intraoperative watertight closure.

2. STUDY DESIGN

This is a prospective, randomized, open-label, multi-center controlled study evaluating the safety and effectiveness of EVICEL as an adjunct to sutured dural closure compared to standard adjunctive dural closure techniques using additional repair sutures only to obtain an intraoperative watertight dural closure. Subjects will be screened and selected from the patient population of approximately 4-8 clinical sites.

Subjects will undergo an elective or urgent posterior fossa or supratentorial procedure (craniectomy or craniotomy). Upon completion of the primary sutured dural repair, the closure will be evaluated for intraoperative CSF leakage with a baseline Valsalva maneuver 20-25 cm H₂O for 5-10 seconds. If a spontaneous leak is apparent immediately after dural closure, no Valsalva will be performed. Subjects who have an identified CSF leak (spontaneous or as identified with the Valsalva) will be enrolled into the study.

A number of 42 paediatric subjects with intra-operative cerebrospinal fluid (CSF) leak following primary suturing of the dura will be randomized to either EVICEL Fibrin Sealant (Human) or to adjunctive dural closure techniques using Additional Sutures only (Control) in a 2:1 allocation ratio and will be stratified by surgical procedure, posterior fossa or supratentorial.

Randomization will be used to avoid bias in the assignment of treatment to each subject, to increase the likelihood that attributes of the subject are balanced across treatment groups, and to enhance the validity of statistical comparisons across treatment groups.

ETHICON will provide each site with computer-generated randomization envelopes, each bearing the subject randomization number, and containing the treatment allocation. Treatment will be assigned randomly to each subject on a 2:1 basis to either EVICEL or additional adjunctive repair sutures only. In the event that a potential subject fails intraoperative criteria, and is not randomized to the study, the unused randomization envelope should be returned to the series, and used for the next subject. Given the difference between the two treatment groups, it will not be possible for the surgeon to be blinded to the treatment. However, to avoid any bias in the conduct of the surgical procedure, randomization should only take place after sutured dural closure and the detection of CSF leakage.

Subjects will be followed post-operatively through discharge and for 30 days (± 3) post-surgery. The incidence of CSF leaks will be assessed within 5 days (± 2 days) and 30 days (± 3 days) post-operatively as detected by any of the following: clinical observation, diagnostic testing or the need for surgical intervention to treat a CSF leak or pseudomeningocele.

3. STUDY ENDPOINTS

The **primary** effectiveness endpoint is the proportion of success (intraoperative watertight closure) in the treatment of intraoperative CSF leakage defined as no CSF leakage from dural repair intraoperatively, during a Valsalva maneuver 20-25 cm H₂O for 5-10 seconds.

For subjects randomized to EVICEL, if a CSF leakage is still apparent after the first EVICEL application, a second treatment (up to two layers) with EVICEL may be applied. The CSF leakage will be re-evaluated with the Valsalva maneuver 20-25 cm H₂O for 5-10 seconds. If watertight closure is not evident after this second Valsalva maneuver, the subject will be deemed a failure and the surgeon may revert to his/her standard of care for closure including the use of other commercially available fibrin sealants (except EVICEL®) or an dural patch. If watertight closure is achieved with EVICEL, no additional adjunct should be used and the subject will be deemed a treatment success.

Subjects randomized to control will receive additional dural sutures as deemed necessary by the surgeon. The CSF leakage will be evaluated with the Valsalva maneuver 20-25 cm H₂O for 5-10 seconds. If watertight closure is not evident after the Valsalva maneuver, the subject will be deemed a failure and the surgeon may revert to his/her standard of care for closure including the use of other commercially available fibrin sealants (except EVICEL) or an dural patch. If watertight closure is achieved, but the surgeon feels that an adjunct (excluding the use of fibrin sealants) is required to assure durability of closure, then such treatment should be applied. This will be considered a treatment success.

In addition, the following **safety/secondary** endpoints will be included in this study:

- Incidence of CSF leakage within 5 days (± 2 days) post-operatively;
- Incidence of CSF leakage within 30 days (± 3 days) post operatively;

The CSF leaks within 5 days (± 2 days) and 30 days (± 3 days) post-operatively will be detected by any of the following: clinical observation, diagnostic testing or the need for surgical intervention to treat a CSF leak or pseudomeningocele.

- Incidence of adverse events, collected from time of randomization, throughout the follow-up period until 30 days (± 3 days) after the procedure;
- Incidence of surgical site infections (SSI) according to National Healthcare Safety Network (NHSN) criteria within 30 days (± 3 days) post-operatively;
- Laboratory tests (complete blood count with differential, liver function tests and electrolytes) at baseline and 5-day (± 2 days) visit.

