2. STUDY OBJECTIVES

The objective of this study is to evaluate the safety and efficacy of EVICEL®, for suture-line sealing in dura-mater closure to obtain intraoperative watertight closure, in paediatric patients undergoing elective or urgent cranial neurosurgery.

The primary efficacy endpoint will be the proportion of success (intraoperative watertight closure) in the treatment of persistent intraoperative CSF leakage following primary suture repair. Intraoperative watertight closure will be defined as no CSF leakage from the dural repair intraoperatively following the randomly assigned treatment with EVICEL® or Control (additional dural sutures), as assessed during a Valsalva maneuver 20-25 cm H₂O for 5-10 seconds.

The secondary/safety endpoints include:

- Safety and tolerability assessments
 - Incidence of CSF leakage within 5 days (± 2 days) post-operatively.
 - Incidence of CSF leakage within 30 days (± 3 days) post-operatively.
 - Incidence of adverse events
 - Incidence of surgical site infections (SSI) according to National Healthcare Safety Network (NHSN) criteria within 30 days (± 3 days) post-operatively.

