6.3 Additional Sutures Only (Control Group)

Subjects randomized to control will receive additional dural repair sutures as deemed necessary by the surgeon to attempt to achieve a watertight closure.

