7. PROCEDURE DATA

Procedure data will be summarized descriptively for subjects in each treatment group in the FAS set to assess comparability of treatment groups. The categorical data will be summarized descriptively by frequencies along with the associated percentages. The continuous data will be presented using summary statistics such as number of subjects, mean, standard deviation, minimum, median and maximum.

The following procedure variables will be analyzed:

- Operative procedure, including type of approach, indication for surgery and tumor location, if applicable;
- Operating room (OR) time;
- Procedure duration (from first incision to closure completion);
- Specification of treatment to which subject is randomized;
- CSF leak determination;
- For patients treated with EVICEL, the following data will be analyzed for first EVICEL application and second treatment of EVICEL (if applicable): method of EVICEL application, number of layers applied, indication of spontaneous leak observation, indication of Valsalva maneuver performed after randomized treatment application (if applicable), indication of CSF leak detection after Valsalva, definition of leak (if applicable), and type of tip used.
- EVICEL application summary data, such as total number of kits used, approximate total amount of EVICEL used, derived volume per kit, and indication of watertight closure observed;
- For patients treated with Additional Sutures, number of sutures applied, indication of spontaneous leak observation, indication of Valsalva maneuver performed after randomized treatment application (if applicable), indication of watertight closure observed, and indication of additional treatment required for durability of the dura closure (suture, collagen, oxidized regenerated cellulose and/or other treatment);
- Indication and specification of standard of care method for rescue therapy applied, such as DuraSeal, BioGlue, other glues, hemostatic matrices, autologous and biologic dural patches;
- Length of subject hospital stay (from hospital admission to hospital discharge, as well as from procedure to hospital discharge).

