8.2 Primary effectiveness analysis

The primary effectiveness endpoint is the proportion of success (intraoperative watertight closure) in the treatment of intraoperative CSF leakage defined as no CSF leakage from dural repair intraoperatively, during a Valsalva maneuver 20-25 cm H₂O for 5-10 seconds.

No formal sample size calculation has been performed for this study. The sample size required for the trial is 42 randomized paediatrics subjects recruited from 6-8 sites within the European Union. This sample size is considered adequate by EMA Paediatric Investigation Plan to summarize the data descriptively.

The primary effectiveness endpoint will be analyzed using the FAS and the PP set. However, the primary analysis will be based on the FAS. The PP analysis will be considered confirmatory.

In all cases, treatment allocation will be based on randomization for the primary effectiveness endpoint using the FAS. If more than two subjects are mis-randomized, then an additional confirmatory analysis based on treatment received will be performed for the primary effectiveness endpoint, using the FAS.

The proportion of successes will be summarized descriptively by treatment group. In addition, a two-sided 95% confidence intervals (CIs) will be reported for the ratio of the proportion of success in the EVICEL group/proportion of success in Control group (P_E/P_C), using the Farrington-Manning score method.

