8.5 Statistical/analytical issues

8.5.1 Handling of dropouts or missing data

For the primary effectiveness endpoint, the analysis for the FAS set will be performed considering missing data as failures; in addition, sensitivity analyses for the FAS set will be performed considering missing data as successes, and, as worst-case, with missing data for the EVICEL group considered as failures and missing data for the Control group considered as successes.

If there are incomplete dates and calculations (e.g. time since procedure) are needed, the following rules are used (no rules will be applied for missing years; this data would normally be expected to be queried):

- Missing date which includes the procedure data: the rules below are followed unless the derived date is pre-procedure, when the derived date will be 1st day after the procedure.
- Missing day: 15th used

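### Does allowing a second EVICEL treatment, against a single tested round of sutures, undermine the planned success ratio?

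*SAP*

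**What the plan says.** SAP 3 and Protocol 7.1.3 describe the same rules. In the sealant arm, "if a CSF leakage is still apparent after the first EVICEL application, a second treatment (up to two layers) with EVICEL may be applied". Closure is then tested again, and only a leak at this second Valsalva makes the subject a failure. For control, sutures are placed and tested once: "If watertight closure is not evident after the Valsalva maneuver, the subject will be deemed a failure". Protocol 6.3 sets no limit on the suturing that precedes this test; sutures are added "as deemed necessary by the surgeon to attempt to achieve a watertight closure".

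Protocol 2 defines the primary endpoint as absence of leakage "following the randomly assigned treatment with EVICEL® or Control (additional dural sutures", so what is assessed is the result of the whole assigned treatment. SAP 8.2 states that "confidence intervals (CIs) will be reported for the ratio of the proportion of success in the EVICEL group/proportion of success in Control group", by the Farrington-Manning score method. There is no hypothesis test, and of the 42 subjects SAP 8.2 says: "This sample size is considered adequate by EMA Paediatric Investigation Plan to summarize the data descriptively".

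Results at each step are also planned. SAP 7 says that for EVICEL patients "the following data will be analyzed for first EVICEL application and second treatment of EVICEL (if applicable", including leak detection after Valsalva (Table 14.1.3.3). The control result is in Table 14.1.3.5. Subject-level detail is in Listings 16.2.5.2 (EVICEL application), 16.2.5.4 (additional sutures) and 16.2.6.1 (primary endpoint).

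**The concern.** An EVICEL subject who leaks at the first post-treatment test can be treated and tested again. A control subject who leaks at the only test is a failure. With equal success per attempt, the arm with two tested attempts finishes ahead, and the ratio alone does not show whether an advantage was present at the first test or came from re-treatment.

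The planned variants of the primary analysis do not separate the two. They cover missing data, the per-protocol set and, if more than two subjects are mis-randomized, treatment received. SAP 8.3 plans no secondary effectiveness analysis. If the ratio were read as the effect of one application against one round of sutures, it could overstate EVICEL.

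**Working it through.** **Inputs.** 42 subjects at 2:1 (SAP 2) give 42 × 2/3 = 28 EVICEL and 42/3 = 14 control. The plan states no power, margin or success rate, so it has no figure of this kind to reproduce. All rates below are assumptions.

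**Effect of re-treatment, no rates assumed.** Each EVICEL subject sealed only on re-treatment adds 1/28 = 3.6 percentage points to P_E. With x sealed at the first test and r more on re-treatment, the final ratio is (x + r)/x times the first-test ratio. For r = 2:
- x = 14: 16/14 = 1.14
- x = 20: 22/20 = 1.10
- x = 24: 26/24 = 1.08

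**Case (a): a control round is one attempt.** Let success be p at the first attempt in both arms. Let a share kp of EVICEL first-test failures be sealed on re-treatment; k combines the yield of the second attempt relative to the first with the share re-treated. Then P_C = p, P_E = p + (1 − p)kp, the first-test ratio is 1.00 and the final ratio is 1 + k(1 − p).

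**Case (b): a control round already holds a second attempt of the same yield.** Protocol 6.3 permits this, since the surgeon may add sutures before the formal test. Then P_C = p + (1 − p)kp as well. The final ratio is 1.00 and the first-test ratio is 1/[1 + k(1 − p)].

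| p | k | (a) final ratio | (b) first-test ratio |
|---|---|---|---|
| 0.2 | 0.25 | 1.20 | 0.83 |
| 0.5 | 0.25 | 1.13 | 0.89 |
| 0.95 | 0.25 | 1.01 | 0.99 |
| 0.2 | 0.5 | 1.40 | 0.71 |
| 0.5 | 0.5 | 1.25 | 0.80 |
| 0.95 | 0.5 | 1.03 | 0.98 |

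The documents do not say which case is nearer the truth. Under (a) the first-test ratio isolates the first attempt. Under (b) it shows a deficit for EVICEL although the two strategies perform equally.

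**What a first-test ratio could discriminate.** Take 14/28 against 7/14 at the first test: 1.00, 95% score interval 0.55 to 2.02. With two more EVICEL subjects sealed on re-treatment, 16/28 against 7/14 gives 1.14 (0.65 to 2.26). The intervals overlap almost entirely. By exact enumeration under case (a), the final interval lies above 1 while the first-test interval does not in 2–4% of trials for k = 0.25 and 4–11% for k = 0.5.

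**Whether a first-test row is well defined.** The EVICEL figure would be an interim result, taken when the surgeon knows re-treatment is available. The control figure would be its final result. Spontaneous leaks also need a counting rule. Table 14.1.3.5 records them separately from watertight closure, so a control subject could leak spontaneously, be sutured further and pass the Valsalva. If that subject counted as a first-test failure, the first-test ratio could exceed the final one. With two such subjects among the seven control successes, it is 14/28 against 5/14 = 0.500/0.357 = 1.40, compared with a final ratio of 1.14. The first-test ratio is therefore not even a guaranteed lower bound.

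**The case for a change.** The strongest counter-argument is that the final ratio is the only planned between-arm estimate and a first-test row would cost little, because the data are collected. Without it, a reader who wants the comparison must build EVICEL first-application success from separate spontaneous-leak and Valsalva items. Watertight closure itself is tabulated for EVICEL only in the overall application summary (Table 14.1.3.4). SAP 8.5.1 states its missing-data rule for the primary endpoint alone: "For the primary effectiveness endpoint, the analysis for the FAS set will be performed considering missing data as failures". In an open-label trial it is better to fix such choices in advance. The effect could also be larger than in the table: if every leaking subject were re-treated and the second attempt were as effective as the first (k = 1), case (a) gives 1.70 at p = 0.3 and 1.20 at p = 0.8. The final interval would then lie above 1 in about 28% to 41% of trials over p = 0.3 to 0.8.

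It is true that no first-test ratio is planned and that computing one needs counting choices. This does not amount to a fault. The k = 1 figures are an upper bound and rest on a control round being a single attempt, which the protocol does not say. Subject-level listings let the step results be traced without combining table margins. Protocol 8.5 does not anticipate missing primary-endpoint data for treated subjects. Adding the row is a matter of preference.

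**Conclusion.** The concern does not hold. The ratio answers the question both documents pose: success of EVICEL with permitted re-treatment against success of additional sutures placed at the surgeon's discretion. The rules are pre-specified and consistent, and following them gives a valid comparison of the assigned strategies.

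The difference in the number of formal tests is real, but its direction is unknown because control suturing is uncapped. Under the assumed values (p = 0.2 to 0.95, k = 0.25 to 0.5), the final ratio is 1.01 to 1.40 in one reading of the control round and 1.00 in the other, where a first-test ratio would read 0.71 to 0.99. A first-test ratio is therefore no fairer than the planned one, and with 28 and 14 subjects it could rarely be told apart from it. The study is descriptive, the step results are already to be reported, and no conclusion in the plan depends on the missing ratio. The one caution is in interpretation: P_E/P_C describes strategies and should not be read as the effect of a single application.
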